#### D.2.b. BREXPIPRAZOLE

Brexipiprazole (Rexulti®) is a serotonin-dopamine activity modulator, with a unique receptor binding profile and low intrinsic D2 activity suggestive of a lower potential than aripiprazole to cause activation-like adverse effects, such as akathisia (McKeage K, 2016). The drug was recently approved by the US FDA for adjunctive therapy with antidepressant treatment (ADT) in patients with major depressive disorder (MDD) and inadequate response to ADT. In two phase III trials, adjunctive oral

brexpiprazole 2 or 3 mg once daily was more effective than monotherapy with ADT in improving depressive symptoms in adults with MDD who demonstrated an incomplete response to previous treatment with ADT (McKeage K, 2016). Adjunctive brexpiprazole was generally well tolerated in clinical trials, which included treatment periods of up to 52 weeks (McKeage K, 2016). There is preliminary evidence that adjunctive treatment with brexpiprazole may represent a strategy for patients with MDD and inadequate response to antidepressant treatment who have symptoms of irritability (Fava M et al, 2016) and anxiety (McIntyre RS et al, 2016).

## E. STUDY RATIONALE

Primary Aim: The primary objective is to investigate whether brexpiprazole (initial dose .5 mg/day titrating to 3 mg/day over 21 days) is superior to placebo when combined with intranasal ketamine in the acute treatment of patients with TRD at two weeks (Day 14), when added to ongoing and stable antidepressant therapy with respect to the study primary outcome measure [change in the SDQ total score].

Secondary Aim 1: The secondary objective #1 is to investigate whether brexpiprazole (initial dose .5 mg/day titrating to 3 mg/day over 21 days) is superior to placebo when combined with intranasal ketamine in the acute treatment of patients with TRD within 48 hours (Day 2), when added to ongoing and stable antidepressant therapy with respect to the study primary outcome measure [change in the SDQ total score].

Secondary Aim 2: The secondary objective #2 is to investigate whether brexpiprazole (initial dose .5 mg/day titrating to 3 mg/day over 21 days) is superior to placebo when combined with intranasal ketamine in the acute treatment of patients with TRD at four weeks (Day 28), when added to ongoing and stable antidepressant therapy with respect to the study primary outcome measure [change in the SDQ total score].

Secondary Aim 3: The secondary objective #3 is to investigate whether brexpiprazole (initial dose .5 mg/day titrating to 3 mg/day over 21 days) is superior to placebo when combined with intranasal ketamine in the acute treatment of patients with TRD at four weeks (Day 28), when added to ongoing and stable antidepressant therapy with respect to the rates of sustained response [50% or greater reduction in the MADRS total score].

Secondary Aim 4: The secondary objective #4 is to investigate whether brexpiprazole (initial dose .5 mg/day titrating to 3 mg/day over 21 days) is superior to placebo when combined with intranasal ketamine in the acute treatment of patients with TRD at Day 2, Day 14, and Day 28, when added to ongoing and stable antidepressant therapy with respect to the study secondary outcome measures [MADRS, HAMD-6, CGI-S, CGI-I].

Secondary Aim 5: The secondary objective #5 is to characterize the safety and tolerability of brexpiprazole or placebo treatment during the acute, 4-week treatment period.

## F. OBJECTIVES

### F.1. PRIMARY AIM OF THE KETAMINE-BREXPIRAZOLE TRIAL

The primary objective is to investigate whether the degree of improvement in SDQ total score on brexpiprazole (initial dose .5 mg/day titrating to 3 mg/day over 21 days) is superior to placebo when combined with intranasal ketamine in the acute treatment of patients with TRD at two weeks (Day 14), when added to ongoing and stable antidepressant therapy with respect to the study primary outcome measure. Superiority will be demonstrated by a statistically significant greater decrease ( $p < 0.05$ , 2-sided) on the SDQ total score for patients receiving brexpiprazole versus placebo therapy.

### F.2. SECONDARY AIMS OF THE KETAMINE-BREXPIRAZOLE TRIAL

The secondary objectives are to:

- Investigate whether brexpiprazole (initial dose .5 mg/day titrating to 3 mg/day over 21 days) is superior to placebo when combined with intranasal ketamine in the acute treatment of patients with TRD within 48 hours (Day 2), when added to ongoing and stable antidepressant therapy with respect to the study primary outcome measure [change in the SDQ total score]. Superiority will be demonstrated by a statistically significant greater decrease ( $p < 0.05$ , 2-sided) on the SDQ total score for patients receiving brexpiprazole versus placebo therapy.
- Investigate whether the degree of improvement in SDQ total score on brexpiprazole (initial dose .5 mg/day titrating to 3 mg/day over 21 days) is superior to placebo when combined with intranasal ketamine in the acute treatment of patients with TRD at four weeks (Day 28), when added to ongoing and stable antidepressant therapy with respect to the study primary outcome measure. Superiority will be demonstrated by a statistically significant greater decrease ( $p < 0.05$ , 2-sided) on the SDQ total score for patients receiving brexpiprazole versus placebo therapy.
- Investigate whether brexpiprazole (initial dose .5 mg/day titrating to 3 mg/day over 21 days) is superior to placebo when combined with intranasal ketamine in the acute treatment of patients with TRD at 4 weeks (Day 28), when added to ongoing and stable antidepressant therapy with respect to the rates of sustained response [50% or greater reduction in the MADRS total score]. Superiority will be demonstrated by a statistically significant greater ( $p < 0.05$ , 2-sided) of sustained response for patients receiving brexpiprazole versus placebo therapy.

- Investigate whether the degrees of improvement in secondary outcome measures [MADRS, HAMD-6, CGI-S, CGI-I] total scores on brexpiprazole (initial dose .5 mg/day titrating to 3 mg/day over 21 days) are superior to placebo when combined with intranasal ketamine in the acute treatment of patients with TRD at Day 2, Day 14, and Day 28, when added to ongoing and stable antidepressant therapy with respect to the study primary outcome measure. Superiority will be demonstrated by a statistically significant greater decrease ( $p < 0.05$ , 2-sided) on the total scores of these secondary measures for patients receiving brexpiprazole versus placebo therapy.
- Characterize the safety and tolerability of brexpiprazole compared to placebo using the following information: vital signs, treatment-emergent adverse events, the CHRT, 12-lead electrocardiogram (ECG), and other laboratory analyses.

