## C. STUDY SYNOPSIS

Title of Study:	A Double-Blind, Placebo-Controlled Study of Brexpiprazole plus Ketamine in Treatment-Resistant Depression (TRD)
Objective:	To evaluate the efficacy, safety, and tolerability of brexpiprazole in combination with intranasal ketamine (40 mg biweekly for 2 weeks and weekly for 2 weeks), compared to placebo, as a rapidly acting treatment for TRD
Methodology:	This is a multi-site, double-blind, placebo-controlled study of the acute efficacy of brexpiprazole or placebo in combination with intranasal ketamine added to ongoing, stable, and adequate antidepressant therapy (ADT) in the treatment of adults with MDD with TRD.
Number of Patients:	52 Patients
Diagnosis and Main Criteria for Inclusion:	Male and female outpatients (aged 18 to 65 years) who meet DSM-5 ( Diagnostic and Statistical Manual of Mental Disorders , Fifth Edition) criteria for MDD, have a current depressive episode of at least 8 weeks, and meet all of the following criteria: 

• <50% response to current antidepressant treatment (at least 8 weeks at an adequate dose, stable dose for at least 4 weeks)

• >1 and <8 failed trials in the current episode as per MGH ATRQ

• MADRS <math>\geq</math> 20 at screening and at baseline

• Good general health

• BMI= 18-35 kg/m^2

• Willing to use birth control if the patient is of child bearing potential

Test Product, Dosage, and Mode of Administration:	Subjects will be randomly assigned to one of two arms in a 1:1 fashion: brexpiprazole 0.5-3 mg/day or placebo for four weeks in combination with bi-weekly administration of intranasal ketamine (40 mg) for two weeks, and then weekly administration of intranasal ketamine (40 mg) for two weeks.
Visit Schedule:	Screening Visit, Baseline visit (Visit 1), Visits 1 and 2 days after the Baseline Visit (Visits 2 and 3), and then every 3 days after that for 26 days, with end of study visit one week after the last double-blind visit.
Primary Outcome Measure:	Symptom improvement will be evaluated by assessing changes in the SDQ.
Secondary Outcome Measures:	MADRS, HAMD-6, CGI-S, CGI-I.

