## N. DATA ANALYSIS

To analyze the primary outcome data, we will use a linear mixed model for the observations taken at baseline, and subsequent visits, with terms for visit, and visit\*treatment for visits other than baseline, the primary contrast of interest being the difference between the two weeks (Day 14) value for active treatment and placebo. To address missing data, we will use all available data and use a restricted maximum likelihood estimation procedure, as implemented by SAS Proc MIXED. The model will include a site, a site\*time effect and a site\*time\*treatment interaction. The latter will be removed if not significant. Number of comorbid medical and psychiatric disorders and duration of illness, as measured prior to randomization, will be included as covariates. For the continuous secondary efficacy variables, the same approach as for the primary efficacy variable will be used for the analysis.

Power analysis: the sample size was chosen to ensure 80% power to detect an effect size of 0.8 on the SDQ between brexpiprazole plus intranasal ketamine treatment and placebo at a two-sided 0.05 significance level. This assumes the randomization of 52 subjects (26 subjects per arm).

O. PROTOCOL SIGNATURE PAGE

I have read this protocol and agree to adhere to the requirements. I will provide copies of this protocol and all pertinent information to the study personnel under my supervision. I will discuss this material with them and ensure they are fully informed regarding the conduct of the study according to 21 CFR parts 50, 54, 56 and 812, 45 CFR 46, to GCP as described in ICH guideline E6 and to hospital Institutional Review Boards.

\_\_\_\_\_  
Clinical Site

\_\_\_\_\_  
Principal Investigator Signature

\_\_\_\_\_  
Date

\_\_\_\_\_  
Principal Investigator  
Printed Name

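### Section F.2 lets any of four secondary efficacy aims count as demonstrated superiority at two-sided p<0.05, whatever the primary shows, and does not say how many of the 12 results in its fourth aim must be significant

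*Combined protocol and SAP*

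**What the plan says.** F.1 names one primary test: change in SDQ total score, brexpiprazole against placebo, "in the acute treatment of patients with TRD at two weeks (Day 14"), at two-sided 0.05.

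F.2 then lists four secondary efficacy aims, each with its own success sentence at two-sided p<0.05:

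1. SDQ at Day 2.
2. SDQ at Day 28.
3. Day 28, "with respect to the rates of sustained response [50% or greater reduction in the MADRS total score"].
4. MADRS, HAM-D6, CGI-S and CGI-I at Days 2, 14 and 28.

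For aims 1, 2 and 4 the sentence begins "Superiority will be demonstrated by a statistically significant greater decrease"; aim 3 is worded almost identically. For aim 4 the decrease must be seen "on the total scores of these secondary measures for patients receiving brexpiprazole versus placebo therapy", with no statement of how many scales or days are needed.

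Section E numbers the same aims (for example "Secondary Aim 1: The secondary objective #1 is to investigate whether brexpiprazole") but does not call the numbering a testing sequence. Section N names the Day 14 contrast as primary and says of the rest: "For the continuous secondary efficacy variables, the same approach as for the primary efficacy variable will be used for the analysis". That fixes the model and says nothing about multiplicity. The synopsis adds nothing on this. The reference list contains a multiple-comparison paper, but no analysis text uses it.

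**The concern.** Many protocols leave secondary endpoints unadjusted and call them supportive. This one says instead that a nominal p<0.05 demonstrates superiority, and it says so separately for each aim. Under its own wording, the trial could miss on SDQ Day 14 and still report superiority as demonstrated on a secondary.

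The open rule for aim 4 adds to this. The number of routes to a claim is 3 + 12 = 15 if each scale and day counts separately, or 3 + 1 = 4 if all 12 results are needed together. As written, that choice could be made after the data are seen.

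**Working it through.** **The plan's own figure.** Section N gives 26 per arm, standardized effect 0.8, two-sided alpha 0.05 and 80% power. Noncentral-t power for a two-sample test at 26 per arm is 80.7%, so the figure reproduces. The documents state no familywise error figure for the secondary aims.

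**Event counted.** No true effect anywhere; primary not significant in favour of brexpiprazole; at least one secondary aim met in its favour. Each single directional result then has a 2.5% chance of a false claim.

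**Limit with no correlation.**
- 15 separate claims: 0.975 × (1 − 0.975^15) = 0.975 × 0.316 = 30.8%.
- Aim 4 needing all 12: 0.975 × (1 − 0.975^3) = 0.975 × 0.0731 = 7.1%. The all-12 event itself is negligible here.

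**With correlation.** The documents give no correlations, so the same value is assumed between scales and between days, from 0.4 to 0.9. Test statistics are simulated as normal. Sustained response is given a correlation of 0.75 with the Day 28 MADRS statistic (also assumed).

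| What aim 4 requires | Correlation 0.4 | Correlation 0.9 |
|---|---|---|
| Any scale on any day | 22% | 6.6% |
| One scale on all three days | 6.4% | 3.6% |
| All four scales on one day | 6.3% | 3.3% |
| All 12 results | 6.2% | 3.2% |
| Aim 4 left out (aims 1-3 only) | 6.2% | 3.2% |

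On the stricter readings, aim 4 adds almost nothing; the 3-6% comes from the three single-result aims.

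**Sensitivity to the model.**
- Patient-level simulation (26 per arm, t-tests in place of the mixed model, Fisher test on an assumed 35% response rate in each arm): 21.9% to 6.1% for 15 claims, and 5.4% to 2.5% for the all-12 reading.
- Wider correlation range, 0.3 to 0.9, with two correlation structures: 25.2% to 4.8% for 15 claims, and 6.6% to 2.2% for the all-12 reading.

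**Benchmark.** One SDQ secondary (Day 2) counted the same way, from the patient-level simulation: 0.0266 − 0.0032 = 2.3% at correlation 0.4, and 0.0266 − 0.0157 = 1.1% at 0.9.

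**What a formal gate would cost.** A gated secondary claim cannot be more likely than a significant primary. Assume true effects of 0.2, 0.4 and 0.8 at Days 2, 14 and 28. Primary power at 0.4 with 26 per arm is 29.3%. The chance of a Day 28 SDQ claim then falls from about 81% ungated to 25-29% (gate, then Holm) or 6-10% (gate, then Day 2 before Day 28). If the effect is 0.8 on all three days, it falls from 81% to 67-73% or 60-73%.

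**The case against.** **The primary inference is sound.** There is one measure, one contrast at Day 14 and no interim look. The other aims are labelled secondary and framed as investigations. With 52 patients, and with K.5 describing a full development programme as the next step, this reads as early-stage work, where formal control over secondaries is often not expected. All of that stands. It answers a complaint that adjustment is missing. It does not answer the wording, which declares what a nominal p-value demonstrates.

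**The large figure depends on the loosest reading of aim 4.** A reader might infer a false-claim rate of about 22%, or 15 planned claims. The documents do not support that. The aim is written in the plural across scales and days, and nothing says that one scale on one day is enough. Every stricter reading examined stays at about 3-6%. What is established is that the success rule is undefined.

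**A reader might also infer that the trial's overall error rate is broken, or that secondaries must be gated on the primary.** Neither follows. The primary keeps its 5% two-sided level. A gate is a trade-off: per Section I.1 the dose reaches 2 mg/day only at Day 14, and D.2.b cites benefit at 2 or 3 mg, so a smaller Day 14 effect is plausible and a gate could block a real Day 28 finding.

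**In the other direction,** the numbering in Section E could be taken as a fixed sequence, with Day 2 first to suit the synopsis aim of testing brexpiprazole "compared to placebo, as a rapidly acting treatment for TRD". The protocol never says so.

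**Conclusion.** The concern holds in a limited form. F.2 is a stated decision rule that allows a secondary aim to demonstrate superiority beside a failed primary, and nothing elsewhere restrains it.

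With no true effect, the chance of such a claim for brexpiprazole is about 3-6% on the stricter readings of aim 4 and about 6-22% only if any scale on any day counts, against about 1-2% for a single SDQ secondary. These figures rest on assumed correlations, normal statistics in place of the mixed model, and an assumed link between sustained response and MADRS (Section N names no test for it). They count only results favouring brexpiprazole. The gap in the text does not depend on any of these assumptions. It should be corrected, but it does not threaten the primary analysis.

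**What to change.** In F.2 and N:

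- Keep SDQ Day 14 as the only formal superiority test.
- Delete the demonstration sentence from all four secondary efficacy aims.
- State that SDQ Day 2, SDQ Day 28, sustained response, and MADRS, HAM-D6, CGI-S and CGI-I by day are supportive, reported with estimates, 95% CIs and nominal, unadjusted p-values.

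This also settles aim 4, since no count of significant results is then needed. It takes no extra patients or assessments and leaves the primary alpha unchanged. The price is that no secondary result can be called a demonstration of superiority, although every estimate is still reported.

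Optional, for the sponsor to decide before unblinding: if a formal claim on SDQ Day 2 or Day 28 is wanted, write a multiplicity rule for it, for example a gate on Day 14 followed by Holm or a fixed order. Under the gate, a false secondary claim when the primary null is true occurs at most 2.5% of the time. The sponsor should weigh that against the loss of Day 28 claims shown in the working.

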## G. STUDY DESIGN

### G.1. OVERVIEW

This is a multi-site, double-blind, placebo-controlled study of the acute efficacy of oral brexpiprazole or placebo combined with intranasal ketamine added to ongoing, stable, and adequate antidepressant therapy (ADT) in the treatment of adults with MDD with TRD. Adequate ADT is defined as a therapeutically sufficient dose for a sufficient treatment period, which would be expected to be effective as listed in the MGH ATRQ.

### G.2. METHODS

Following a washout period for patients on prohibited psychotropic agents, 52 eligible subjects will be randomly assigned to one of two arms in a 1:1 fashion: brexpiprazole (initial dose .5 mg/day titrating to 3 mg/day over 21 days) or placebo for four weeks in combination with bi-weekly administration of intranasal ketamine (40 mg) for two weeks, followed by weekly administration of intranasal ketamine (40 mg) for two weeks. All subjects will be followed for 28 days to examine the efficacy and tolerability of the study drugs' effects.

### G.3. STUDY DESIGN

The study will consist of a screening period and a randomization period. Patients who meet eligibility during the screening period will be randomized to double-blind treatment with brexpiprazole plus intranasal ketamine treatment or placebo as described above.

## H. STUDY POPULATION

### H.1. NUMBER OF SUBJECTS

52 subjects will enter the double-blind treatment phase of the study. This trial will be conducted according to the U.S. FDA guidelines and the Declaration of Helsinki. IRB- approved written informed consent will be obtained from all patients before any protocol-specified procedures are carried out. The subjects will be drawn from an outpatient sample of patients with MDD, diagnosed with the use of the Structured Clinical Interview for DSM-5 Axis I Disorders–Patient Edition (SCID-5), currently on an adequate dose of antidepressant therapy, as defined by the MGH ATRQ, for at least 8 weeks, with the dose being stable for at least 4 weeks, and with TRD (see definition below). For entry into the study, all inclusion criteria must be met, and none of the exclusion criteria can be met.

## H.2. SUBJECT ELIGIBILITY

### H.2.a. INCLUSION CRITERIA

A subject will be eligible for inclusion only if all of the following criteria are met:

1. Male or female, 18 to 65 years of age, inclusive, at screening.
2. Able to read, understand, and provide written, dated informed consent prior to screening. Participants will be deemed likely to comply with study protocol and communicate with study personnel about adverse events and other clinically important information.
3. Diagnosed with MDD, single or recurrent, and currently experiencing a major depressive episode (MDE) of at least eight weeks in duration, prior to screening, according to the criteria defined in the Diagnosis and Statistical Manual of Mental Disorders, Fifth Edition (DSM-5). The diagnosis of MDD will be made by a site psychiatrist and supported by the SCID-5. The diagnosis will be confirmed by remote, independent raters from the MGH CTNI (Clinical Trials Network and Institute) with a SAFER interview.
4. Has a history of TRD during the current MDE, as assessed by the investigator and remote centralized rater using the MGH ATRQ. TRD is defined as failure to achieve a satisfactory response (e.g., less than 50% improvement of depression symptoms), as perceived by the participant, to at least 2 “treatment courses” during the current episode of a therapeutic dose of an antidepressant therapy of at least 8 weeks duration (including the current ADT). The adequacy of dose and duration of the antidepressant therapy will be determined as per the MGH ATRQ criteria. The TRD status will be confirmed by remote, independent raters from the MGH CTNI who will administer the MGH ATRQ, via teleconference, between the screening visit and the baseline visit. Participants must currently be on a stable (for at least 4 weeks) and adequate (according to the MGH ATRQ) dose of ongoing antidepressant therapy (any antidepressant therapy, with the exception of MAOIs or antipsychotics), of which total duration must be at least 8 weeks.
5. Meet the threshold on the total MADRS score of  $\geq 20$  at both the screen visit and the baseline visit (Day -7/-28 and Day 0), and as confirmed by the remote centralized MGH CTNI rater between the screen visit and the baseline visit.

6. In good general health, as ascertained by medical history, physical examination (PE) (including measurement of supine and standing vital signs), clinical laboratory evaluations, and ECG.
7. If female, a status of non-childbearing potential or use of an acceptable form of birth control per the following specific criteria:
  - a. Non-childbearing potential (e.g., physiologically incapable of becoming pregnant, i.e., permanently sterilized (status post hysterectomy, bilateral tubal ligation), or is post-menopausal with her last menses at least one year prior to screening); or
  - b. Childbearing potential, and meets the following criteria:
    - i. Childbearing potential, including women using any form of hormonal birth control, on hormone replacement therapy started prior to 12 months of amenorrhea, using an intrauterine device (IUD), having a monogamous relationship with a partner who has had a vasectomy, or is sexually abstinent.
    - ii. Negative urinary pregnancy test at screening, confirmed by a negative urinary pregnancy test at randomization prior to receiving study treatment.
    - iii. Willing and able to continuously use one of the following methods of birth control during the course of the study, defined as those which result in a low failure rate (i.e., less than 1% per year) when used consistently and correctly: implants, injectable or patch hormonal contraception, oral contraceptives, IUD, double-barrier contraception, sexual abstinence. The form of birth control will be documented at screening and baseline.
8. Body mass index between 18-35 kg/m^2.
9. Concurrent psychotherapy will be allowed if the type (e.g., supportive, cognitive behavioral, insight-oriented, et al.) and frequency (e.g., weekly or monthly) of the therapy has been stable for at least three months prior to screening and if the type and frequency of the therapy is expected to remain stable during the course of the subject's participation in the study.
10. Concurrent hypnotic therapy (e.g., with zolpidem, zaleplon, melatonin, benzodiazepines or trazodone) will be allowed if the therapy has been stable for at least 4 weeks prior to screening and if it is expected to remain stable during the course of the subject's participation in the study. Patients can also continue treatment with benzodiazepines used for anxiety if therapy has been stable for at least 4 weeks prior to screening and if it is expected to remain stable during the course of the subject's participation in the study.

